### ***STATISTICAL ANALYSIS***

An independent t-test or Wilcoxon rank-sum test was used to compare groups at each time point. Categorical variables were compared using the Chi-square test or Fisher's exact test. Within-group comparisons were performed using paired t-tests. To appropriately account for repeated measurements and missing data, a Linear Mixed Model (LMM) was employed for the primary outcomes (VO2peak and VO2peak%), allowing for unbiased parameter estimation under the Missing At Random (MAR) assumption. Missing data were handled using maximum likelihood (ML) estimation within the LMM framework. Statistical analyses were conducted using R (version 4.2.1; R Core Team). A two-tailed  $P \leq .05$  was considered significant.

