#### ***Postoperative telerehabilitation (PTR) program IG only***

The IG group received PTR support via a mobile instant messaging application (KakaoTalk; Kakao) three times per week for 4 wk. The PTR program monitored adherence, provided feedback, and adjusted exercise intensity as needed. When retraining or exercise intensity adjustment was needed, education was delivered via text messages, photos, or videos through

a mobile messenger. For participants unfamiliar with the designated mobile messenger, the app was installed and training was provided, considering digital literacy challenges often observed in older adults. However, if participants still had difficulty using the messenger despite training, phone calls were used instead. Two respiratory physiotherapists provided remote supervision through weekly structured messages. The specific instructions and questions provided via messenger included the following:

- 1) Have you achieved your prescribed exercise goals over the past 2 days?
- 2) Was the target heart rate on the fitness tracker maintained well during aerobic exercise?
- 3) Were there any difficulties while performing each exercise?
- 4) Did you write a self-exercise diary after completing the exercise?
- 5) Do you have any further questions?

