### ***CG intervention***

Participants in the CG received a second educational session at 8 wk post-surgery at the rehabilitation center. Apart from these two educational sessions, no further communication was provided. Both groups were instructed to maintain their prescribed exercise routines at least three times per week during the 4-wk follow-up period.

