### ***OUTCOME MEASURES***

Outcomes were assessed at four time points in the two rehabilitation centers: preoperatively and at 4 (baseline), 8 (post-intervention), and 12 wk (follow-up) postoperatively. Primary outcomes included VO2peak and predicted VO2peak %, calculated using Hansen's formula based on CPX performed on a treadmill using a cardiac stress system (Q-Stress; Mortara) with a treadmill (TM-55; Mortara). Gas exchange analysis was performed using a metabolic cart (Quark CPET; Cosmed). Secondary outcomes included ventilatory efficiency (VE/VCO2 slope), forced vital capacity (FVC), forced expiratory volume in 1 sec (FEV1), peak expiratory flow (PEF), MIP, grip strength, skeletal muscle index (SMI), body mass index

(BMI), and whole-body phase angle. SMI and whole-body phase angle were measured using a bioelectrical impedance analysis device (S10; InBody) with electrodes attached to the wrist and ankle after 3 minutes of supine rest. The SMI was calculated by dividing skeletal muscle mass (kg) by height squared (m^2). FVC, FEV1, PEF, and MIP were assessed using a desktop spirometer (Pony FX; Cosmed) following standardized procedures. Grip strength was measured using a handheld dynamometer (Jamar Plus+, Sammons Preston). Psychological well-being and quality of life were assessed using the Hospital Anxiety and Depression Scale (HADS) and the EuroQol 5-dimension questionnaire (EQ-5D-5L). Adherence to the home-based PR program was recorded in a diary. Daily step counts were recorded using a fitness tracker and extracted from the Samsung Health app on each participant's personal mobile phone. To minimize measurement errors, the average step count was calculated for each week, excluding days with the highest and lowest step counts.

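### Continuous secondary outcomes are compared between arms only by unadjusted per-visit tests: the 4-week value is not used at 8 or 12 weeks, and no missing-data method is stated

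*Combined protocol and SAP*

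**What the plan says.** OUTCOME MEASURES sets four assessments: "preoperatively and at 4 (baseline), 8 (post-intervention), and 12 wk (follow-up) postoperatively". Its list of secondary outcomes ("Secondary outcomes included ventilatory efficiency" and so on) has nine continuous measures: VE/VCO2 slope, FVC, FEV1, PEF, MIP, grip strength, SMI, BMI and phase angle. HADS and EQ-5D-5L are described in the same section.

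STATISTICAL ANALYSIS does not assign tests to classes of outcome. Its statements that bear on continuous data are:

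- Between arms: "An independent t-test or Wilcoxon rank-sum test was used to compare groups at each time point". No covariate and no change score is named.
- Within arms: "Within-group comparisons were performed using paired t-tests".
- Repeated measures: "a Linear Mixed Model (LMM) was employed for the primary outcomes", namely VO2peak and VO2peak%.
- Missing data: "Missing data were handled using maximum likelihood (ML) estimation within the LMM framework".

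No other section gives a model or a missing-data rule for the secondary outcomes.

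**The concern.** Read as written, only the first two methods reach the secondary outcomes. The 4-week values are compared between arms as one of the time points, but they do not enter the 8- or 12-week arm comparison, either as a covariate or through a between-arm comparison of change. The paired tests use two visits but do not compare the arms. The plan justifies the mixed model by repeated measurements and missing data, and both reasons apply equally to the secondary outcomes, which come from the same patients at the same visits.

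Three things are at stake:

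1. Precision is lost whenever the 4-week value predicts the later one.
2. A chance imbalance at 4 weeks stays in the later estimate.
3. A per-visit test uses only patients seen at that visit. It can be biased if missingness depends on the 4-week value, whereas a likelihood model containing that value remains valid under the missing-at-random assumption the plan already adopts.

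**Working it through.** **The plan's own figure.** SAMPLE SIZE AND RANDOMIZATION gives effect size 0.74, alpha 0.05, power 0.80 and a required total of 60. A two-sided two-sample t-test (noncentral t) gives power 0.791 at 29 per arm and 0.805 at 30 per arm, so 60 is reproduced. That calculation concerns VO2peak and is not in dispute.

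**Inputs.** 64 were randomised 1:1, taken as 32 per arm. The documents give no correlation ρ between the 4-week and later values, no effect size for a secondary outcome and no dropout figure. I assume ρ = 0.3 to 0.8 and a true difference of 0.5 SD.

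**Precision, complete data.** The unadjusted SE is √(2/32) = 0.25 SD. Adjustment multiplies it by √(1 − ρ²). Unadjusted power is 0.504 on 62 df; adjusted power uses 61 df.

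| ρ | SE ratio | Power |
|---|---|---|
| none (unadjusted) | 1 | 0.504 |
| 0.3 | 0.954 | 0.541 |
| 0.5 | 0.866 | 0.623 |
| 0.7 | 0.714 | 0.787 |
| 0.8 | 0.600 | 0.907 |

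**Precision, with missing visits.** Assume that each arm of 32 loses 2 before 8 weeks and 2 more before 12 weeks (30, then 28 seen). Take equal correlations between visits and a model with a common 4-week mean, using its generalised least squares variance. Over ρ = 0.3 to 0.8, power rises from 0.478 to 0.514–0.887 at 8 weeks and from 0.451 to 0.488–0.869 at 12 weeks.

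**Chance imbalance.** The SE of the 4-week difference is also 0.25 SD, so 0.5 SD or more is a two-SE event with probability 0.0455 per outcome. For at least one of nine outcomes it is 1 − 0.9545⁹ = 0.34 if they are independent, and less if they are positively correlated. Given an imbalance b and no treatment effect, the raw follow-up difference has mean ρb and SD 0.25√(1 − ρ²), and the test rejects beyond about 2.00 × 0.25 = 0.50 SD.

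- At b = 0.5 and ρ = 0.8 the mean is 0.40 and the SD 0.15, so the upper-tail probability is about 0.25. At ρ = 0.3 the rejection rate is about 0.07.
- Simulation with estimated SDs gives 0.08 to 0.27 for the same cases.
- At a typical imbalance of 0.25 SD the simulated rate is 0.029 to 0.049. Averaged over randomisations it is 0.05.

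**Selective loss.** As an extreme case, suppose one arm loses the 4 of its 32 patients with the lowest 4-week values. By the truncated normal, the mean 4-week value of those retained rises by 0.235 SD, so the raw later difference shifts by 0.235ρ: 0.07 SD at ρ = 0.3 and 0.19 SD at ρ = 0.8. Losing the lowest 2 gives 0.04 to 0.10 SD.

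**Paired tests.** If both arms truly change by the same amount and each paired test has power p, exactly one arm is significant with probability 2p(1 − p). With 30 per arm this is 0.026 (change 0.5 SD, ρ = 0.8), 0.302 (0.2 SD, ρ = 0.5) and 0.497 (0.3 SD, ρ = 0.7). These tests cannot stand in for an arm comparison.

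**The case against.** The strongest reply is that this is a choice between valid methods. With complete data the raw test holds its 5% error rate on average, the outcomes are secondary, and the primary outcomes already have a repeated-measures model. That stands, and it limits the point to a recommended improvement.

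The figures also rest on assumed inputs, and the gain at low correlation is slight. The SE ratio above ignores the cost of estimating the covariate slope, about 1/60 of the variance: at ρ = 0.3 the ratio becomes 0.954 × √(1 + 1/60) ≈ 0.962 and power about 0.535 instead of 0.541. The correction is right but too small to matter.

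The imbalance and missing-data cases are unfavourable ones. A 0.5 SD imbalance is uncommon, and nine independent outcomes is implausible when FVC, FEV1 and PEF come from one spirometer. No missing secondary data are documented, and the 0.07 to 0.19 SD shift is smaller than one SE of the comparison (√(1/28 + 1/32) = 0.26 SD). All of this is fair, so these cases should be read as bounds.

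The sentence on maximum likelihood might be meant generally, but its wording ties it to the mixed model, which is named for the primary outcomes only. The paired tests are labelled within-group and no efficacy claim is attached to them, so misreading them is a risk and not a stated use.

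Finally, the 4-week visit is a safe baseline only if no arm difference preceded it. The documents do not state when randomisation took place, and the section on preoperative training does not say which arms received it. The one arm difference they describe, "The IG group received PTR support via a mobile instant messaging application", belongs to the postoperative programme. The fix has to allow for this uncertainty.

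**Conclusion.** The concern holds. The 8- and 12-week arm comparisons of the continuous secondary outcomes are stated only as unadjusted per-visit tests, and no missing-data method covers them. The cost is mainly precision, and it may be small or large depending on a correlation the documents do not give. Chance imbalance and baseline-dependent dropout are further exposures of uncertain size. Nothing here invalidates the raw tests with complete data. It is an improvement worth making, not an error that undermines the trial.

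**What to change.** 1. Confirm when randomisation took place and that care was the same in both arms up to the 4-week visit.
2. If so, extend the mixed model to each continuous secondary outcome that has a 4-week value. Use the 4-, 8- and 12-week values as responses, with a 4-week mean common to both arms, time, group-by-time terms at 8 and 12 weeks, site, and an unstructured covariance over the three visits.
3. If not, use ANCOVA or a mixed model adjusted for the last value before randomisation, which is the preoperative one if randomisation preceded surgery.
4. Report the adjusted between-arm difference with its confidence interval in place of the raw tests. The 8-week difference is the main contrast. The 12-week difference should be read as follow-up, because "Participants in the CG received a second educational session at 8 wk post-surgery at the rehabilitation center".
5. Fit by REML with Kenward-Roger or Satterthwaite degrees of freedom. In a three-parameter ANCOVA on 64 patients, the ML variance with a normal critical value rejects beyond 1.96 × √(61/64) = 1.91 on a t scale with 61 df, a true error rate of about 0.060.
6. For bounded scores such as HADS, add a rank-based ANCOVA or a bootstrap check. Leave out diary adherence, and step counts if they have no 4-week value.
7. State how missing secondary data are handled. Preferably, show within-arm changes descriptively without P values; the main point does not depend on this.

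The cost is modest extra work in R, where a mixed model is already fitted for the primary outcomes, and no new data. The document is written in the past tense, so if the analysis is specified after the data were seen it should be labelled post hoc.

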## ***SAMPLE SIZE AND RANDOMIZATION***

The sample size was calculated using G\*Power (version 3.1.9.6) based on an estimated between-group difference in  $\text{VO}_{2\text{peak}}$  of 3.4 mL/kg/min after the intervention. This estimate was derived from previously published data, where the post-intervention  $\text{VO}_{2\text{peak}}$  values were 23.3 mL/kg/min in the exercise group and 19.0 mL/kg/min in the control group. A power analysis using an effect size of 0.74, a significance level of 0.05, and power of 0.80 determined the required sample size. Based on a power analysis, the required number of participants was 60. To account for an anticipated dropout rate, we screened 96 patients. A total of 64 participants were ultimately randomized. Participants were randomly assigned 1:1 to an intervention group (IG) or a control group (CG) using a central randomization method.

A single individual, uninvolved in the study, managed the process to ensure allocation concealment. An independent statistician generated a randomization table using the R package “blockrand” (version 4.1.3). The block size and seed number were blinded before being provided to the randomization manager. To maintain balance between the groups, a blocked randomization method was chosen, considering the small sample size. Equal block sizes were used across all sites to ensure consistency in the allocation process.

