#### ***Postoperative home-based PR program***

At 4 wk post-surgery (baseline), both groups attended a one-time educational session on standardized home-based PR, conducted by a respiratory physiotherapist at the rehabilitation center. The program was delivered through an educational booklet (Appendix file), which provided detailed information on the rationale, procedures, and precautions for each exercise. Furthermore, QR codes linking to instructional photographs and videos were included. The PR program comprised flexibility exercises, aerobic exercises, resistance training, and continued RMT.

Flexibility exercises targeted limb and trunk mobility, performed three times per week. Stretching intensity was self-paced, held for 10 to 15 sec per stretch, and repeated three times per session. Participants performed neck and arm stretches while seated and leg stretches while standing. For aerobic exercise, a recumbent cycle ergometer (706R; Egojin), installed at each participant's home, was used. Sessions occurred three times per week for 40 minutes, including warm-up and cool-down phases. Intensity was based on cardiopulmonary exercise testing (CPX), starting at 40% of heart rate reserve (HRR) and progressing to 70% of HRR, monitored using a fitness tracker (Galaxy Fit2; Samsung). Resistance training consisted of upper and lower limb strengthening exercises using adjustable elastic bands (TheraBandTM; Akron). Participants performed resistance exercises three times per week, with three sets of 15 repetitions per exercise. Respiratory muscle training continued postoperatively using an IMT/PEP device. Participants started at 30% of MIP, increasing to 50% as pain decreased. Each session included 10 repetitions per set, with 10 sets daily.

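### Within-arm paired t-tests are planned at the general .05 threshold without a descriptive label, and for the secondary outcomes they are the only planned analysis of change

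*Combined protocol and SAP*

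**What the plan says.** The Statistical Analysis section lists three kinds of comparison for continuous outcomes:

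- **Between groups:** an independent t-test or Wilcoxon rank-sum test at each time point.
- **Within groups:** "Within-group comparisons were performed using paired t-tests". The outcomes and pairs of visits are not named.
- **Repeated measures:** an LMM, limited to VO2peak and VO2peak %. No group-by-time term or contrast is written out.

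The section closes with a single two-tailed threshold of .05, at or below which a result "was considered significant". No test is exempted, and the paired tests are not called descriptive.

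The arms share the exercise program. According to the section on the postoperative home-based program, "At 4 wk post-surgery (baseline), both groups attended a one-time educational session on standardized home-based PR". The section on the control group (CG) intervention tells both arms to keep exercising at least three times a week. Messenger support goes to the IG only; the CG has a second education session at week 8.

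**The concern.** The randomised question is whether remote support adds to a home program that both arms receive. A paired test within one arm asks whether that arm changed at all, and so mixes any effect of the support with that of the shared program. Recovery from surgery probably adds to the change in both arms, although that is an inference from the setting and not a figure in the document.

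With a significance threshold attached to each arm's test, a table can show a significant gain in the IG and none in the CG. A reader may then take that as evidence for telerehabilitation. It is not: two P values on either side of .05 do not test the difference between arms.

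The gap is widest for the secondary outcomes, such as the VE/VCO2 slope, spirometry, MIP, grip strength, body composition, HADS and EQ-5D-5L. They have no LMM. Their between-group tests compare levels at each visit, and their only analysis of change is the paired test, which does not compare arms.

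A lesser point is that a paired test uses only patients seen at both visits, whereas the LMM uses all available data under MAR. For the primary outcomes the two analyses can therefore describe different sets of patients.

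**Working it through.** **Inputs.** From Sample Size and Randomization: "A power analysis using an effect size of 0.74", with "a significance level of 0.05, and power of 0.80 determined the required sample size"; "the required number of participants was 60"; "A total of 64 participants were ultimately randomized". Allocation is 1:1, so I take 32 per arm. The between-group difference is given as 3.4 mL/kg/min, but the cited means of 23.3 and 19.0 differ by 4.3. The SD of within-arm change and the correlation between visits are not given and have to be assumed.

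**The plan's own figure.** A two-sided two-sample t-test (noncentral t) with d = 0.74 and alpha 0.05 has power 0.791 at 29 per arm and 0.805 at 30 per arm. The required total is 2 × 30 = 60, which reproduces the plan.

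**Discordance when the arms do not differ.** Let both arms have the same true standardised change δ (mean change divided by SD of change), and let p be the power of the paired t-test in one arm: noncentral t, n − 1 = 31 degrees of freedom, noncentrality δ√32. The arms are independent, so

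- P(only IG significant) = p(1 − p)
- P(exactly one arm significant) = 2p(1 − p)

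The maxima are 0.25 and 0.50, both at p = 0.50.

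| δ | p per arm | only IG | exactly one arm |
|---|---|---|---|
| 0 | 0.050 | 0.048 | 0.095 |
| 0.2 | 0.195 | 0.157 | 0.314 |
| 0.3 | 0.376 | 0.235 | 0.469 |
| 0.358 | 0.500 | 0.250 | 0.500 |
| 0.5 | 0.782 | 0.170 | 0.341 |
| 0.6 | 0.908 | 0.084 | 0.167 |
| 0.74 | 0.982 | 0.018 | 0.036 |
| 1.0 | 1.000 | <0.001 | <0.001 |

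Simulation (100,000 runs, 32 per arm) at δ = 0, 0.2, 0.358, 0.5 and 0.74 gave 0.094, 0.312, 0.498, 0.339 and 0.035 for exactly one arm. In the same runs a direct between-group t-test of change rejected in 0.048 to 0.050.

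**On the VO2peak scale.** SD of change = SD × √(2(1 − ρ)), and the peak lies at 0.358 × SD of change.

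| SD source | ρ (assumed) | SD of change | gain at the peak (mL/kg/min) |
|---|---|---|---|
| 3.4/0.74 = 4.6 | 0.5 | 4.6 | 1.6 |
| | 0.7 | 3.6 | 1.3 |
| | 0.9 | 2.1 | 0.7 |
| 4.3/0.74 = 5.8 | 0.5 | 5.8 | 2.1 |
| | 0.7 | 4.5 | 1.6 |
| | 0.9 | 2.6 | 0.9 |

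With SD 4.6 and ρ = 0.7, shared gains of 1.0, 1.3 and 1.5 give about 45%, 50% and 46% for exactly one arm. A shared gain of 2.5 gives about 6% (about 3% IG only), and 3.0 gives 0.8%.

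**The case against.** The strongest reply is that the error lies in a possible misreading, not in the plan. Whether an arm changed is a legitimate question in itself. The between-group comparison comes first in the Statistical Analysis section, at every time point, and the primary outcomes also have an LMM. A reader might infer that the randomised comparison is missing, or that efficacy will be judged by setting one arm's P value against the other's. The document supports neither inference.

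The size is also open to challenge. The 50% figure is a maximum, needs per-arm power of one half, and counts discordance in both directions; the pattern favouring the IG cannot exceed 25%. A reader might conclude that the error rate is generally far above 5%. It is not. The IG-only rate is about 5% at no change (about 2.4% if only improvements count) and is back to about 5% at δ = 0.65. If both arms improve substantially, both tests are significant and the discordance disappears.

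All of this stands, and it limits the point. Two things remain. The plan does not label the paired tests descriptive, and for the secondary outcomes it offers no between-arm analysis of change that a reader could turn to instead.

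**Conclusion.** The point holds in a limited form, as a cheap improvement. The paired tests share the general threshold with no statement of their role, and they do not address the randomised question. The primary outcomes are largely protected by the planned LMM. The secondary outcomes have between-group tests at each visit but no between-arm contrast in change.

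Under equal true change in both arms, the chance of a misleading IG-only result runs from about 5%, through a maximum of 25%, to near 0. Where this trial falls in that range cannot be determined from the document, because the SD of change is not reported. The rates assume 32 complete pairs per arm, normally distributed changes and independent arms. The mL/kg/min values rest further on the assumed correlation and on which difference, 3.4 or 4.3, lies behind d = 0.74; those two figures need reconciling in their own right. No sample size or primary estimate changes.

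**What to change.** 1. Remove the within-arm P values. Report within-arm mean change with a 95% CI and label it descriptive.
2. State that every efficacy conclusion rests on the between-group contrast, IG minus CG, in change from week 4.
3. For VO2peak and VO2peak %, take that contrast from the planned LMM and write out the group-by-time term.
4. For the secondary continuous outcomes, either extend the same model or use a baseline-adjusted (ANCOVA) comparison with the week-4 value as covariate.

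**Cost.** Items 1 to 3 need only wording, as the primary model is already planned. Item 4 needs some extra analysis, since no model is planned for those outcomes, but no new data. The tables lose their within-arm P values.

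### The primary mixed model is fitted by maximum likelihood with no small-sample correction; with 64 patients this can lift the nominal 5% test to about 5.4% (t reference) or 5.8% (normal reference), and REML removes ML's share at almost no cost

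*Combined protocol and SAP*

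**What the plan says.** The STATISTICAL ANALYSIS section of the combined protocol and SAP says that "a Linear Mixed Model (LMM) was employed for the primary outcomes", which are VO2peak and its percent-predicted value. The stated reason is repeated measurements and missing data, with the model "allowing for unbiased parameter estimation under the Missing At Random (MAR) assumption". The next sentence names the estimator: "Missing data were handled using maximum likelihood (ML) estimation within the LMM framework". Significance is two-tailed at .05, and the software is R 4.2.1.

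REML does not appear. The section also leaves out the fixed effects, the covariance structure, the degrees-of-freedom method and the R package.

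Under SAMPLE SIZE AND RANDOMIZATION, "A total of 64 participants were ultimately randomized", allocated 1:1. Dropout is anticipated, but no rate is given. Under OUTCOME MEASURES, assessments are "preoperatively and at 4 (baseline), 8 (post-intervention), and 12 wk (follow-up) postoperatively"; the documents do not say which of these enter the model.

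**The concern.** ML estimates variance components as if the mean parameters were known. In a small trial this biases the variances downward and, with them, every standard error in the model. The usual remedy is REML with a small-sample degrees-of-freedom method.

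The plan ties ML to the handling of missing data, but that purpose does not call for it. REML is also likelihood-based, uses the same incomplete records, and is equally valid under MAR.

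At stake is the calibration of the only model specified for the primary outcomes. If unadjusted ML standard errors feed the test, its P values are slightly too small, and nothing else in the plan offsets that.

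**Working it through.** **Inputs.** N = 64 randomized, 1:1, two-tailed .05, ML (all from the documents). Assumptions, because the documents are silent: the tested contrast is group by time, with two arm means per visit (p = 2); data are complete unless stated otherwise; the reference distribution is either t or normal.

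**1. The plan's own figure.** The sample-size section reports "A power analysis using an effect size of 0.74, a significance level of 0.05, and power of 0.80", and says that "the required number of participants was 60". A two-sided two-sample t-test with noncentral t gives 30 per arm, 60 in total, with power 0.805. The figure reproduces.

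**2. Size of the ML bias.** With complete data, the ML variance is (N − p)/N times the unbiased one.
- Variance ratio: 62/64 = 0.969, so 3.1% too small.
- Standard-error ratio: sqrt(62/64) = 0.984, so 1.6% too small.

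**3. Effect on the test.** Type I error = 2 × P(t with N − p df > c × sqrt((N − p)/N)), where c is the critical value used. The REML rows have no shrinkage factor.

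| N = 64, p = 2 | t(62) reference | 1.96 reference |
|---|---|---|
| ML, unadjusted | 5.36% | 5.83% |
| REML | 5.00% | 5.45% |
| Due to ML | 0.36 points | 0.38 points |

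The normal reference by itself costs 5.45 − 5.00 = 0.45 points, and REML alone does not remove that. If the model has a random intercept and uses three or four visits, the change contrast has more degrees of freedom. ML then gives 5.37% with t at either number of visits; with 1.96 it gives 5.60% (three visits) or 5.52% (four).

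**4. What larger figures would need.**

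| Evaluable N | p | ML, t reference | ML, 1.96 reference |
|---|---|---|---|
| 64 | 3 | 5.55% | 6.04% |
| 64 | 4 | 5.75% | 6.25% |
| 56 | 2 | 5.41% | 5.95% |
| 56 | 4 | 5.86% | 6.45% |
| 50 | 2 | 5.46% | 6.08% |
| 50 | 4 | 5.97% | 6.65% |

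In this grid, 6% or more requires a normal reference together with extra mean parameters, loss of patients, or both. The documents state none of these. Nor do the p = 3–4 rows carry over to a within-patient change contrast. In random-intercept fits to simulated data (64 patients, three visits), adding two between-patient covariates as main effects left the ML/REML standard-error ratio for group by time at 0.984.

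**5. Dependence on software.** Complete simulated data with 64 patients and three visits were fitted in R 4.3.3 (the trial used 4.2.1).
- nlme `lme`, default summary: group-by-time standard error 0.1893 under ML and 0.1893 under REML. With the adjustment switched off, ML gave 0.1863, and 0.1863/0.1893 = 0.984.
- nlme `gls`: ML and REML also matched.
- lmerTest with `REML=FALSE`: standard errors 0.984 times those under REML.

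The bias therefore reaches the P value with some R routines and not with others. Simulated rejection rates (400 to 1,500 runs) are too coarse to resolve a 0.4-point difference: at 1,500 runs the Monte Carlo standard error is sqrt(0.05 × 0.95/1500), about 0.56 points. The conclusion rests on the formula and the standard-error ratios.

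**The case against.** The strongest objection is that the inflation may not exist. The sentence on ML explains how incomplete records were used; that the tests rested on uncorrected ML standard errors is an inference. Default nlme output would already have corrected them in the settings checked, and the package is not named. This stands, and it makes the point conditional. It does not remove it: two analysts following the same text could report different primary P values, and a better-calibrated method is available at no loss in handling missing data.

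The second objection is materiality. A shift of about 0.4 points matters only to a P value just below .05. This also stands, and it fixes the severity as minor.

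Some stronger readings are tempting but unsupported:
- *The test runs at 6.5% because of ML.* That level needs a normal reference plus covariates or dropout that the documents do not state, and part of it is not due to ML at all.
- *The error always favours telerehabilitation.* The test is two-tailed. Under the null, the 0.36-point excess splits into about 0.18 points toward each arm.
- *ML contradicts the claim of unbiasedness.* That clause most naturally concerns the mean effects under MAR. With complete data, ML and REML gave the same treatment contrast; only the variance estimates differ.
- *The primary confidence interval is too narrow.* The plan specifies no confidence interval, only P values.

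**Conclusion.** The point holds in a limited form. The plan names ML for its primary model and gives no small-sample correction. Unless the software rescales the standard errors, those for a group-by-time contrast with 64 patients are about 1.6% too small, and the nominal two-tailed 5% test runs at about 5.4% (t reference) or 5.8% (normal reference). ML contributes about 0.4 points in either case.

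These figures assume complete data and two arm means per visit, and that group by time is the tested contrast, which the plan does not say. Which R routine was used cannot be told from the documents, so whether the inflation occurred is unknown. The excess favours declaring a difference in either direction. Severity is minor: a better method exists and is cheap to adopt, but this would not by itself overturn a clear result.

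**What to change.** Replace the sentence on ML with:

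> The LMM will be fitted by restricted maximum likelihood (REML) with Kenward-Roger or Satterthwaite degrees of freedom; missing outcomes are handled by the same likelihood under MAR.

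Both parts are needed. REML removes the 0.4 points due to ML, and the degrees-of-freedom method removes the part due to a normal reference. With complete data and a t reference, the test is then at 5.0%. State the fixed effects, covariance structure and R package alongside, so that the analysis can be reproduced.

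The document is written in the past tense. If the analysis is already done, refit the primary model this way, report that result, and say which estimator and package produced the existing one.

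The cost is one sentence, a software option and, if needed, one refit; no new data are required. The downside is that P values become slightly less favourable.
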